**Table 1: Visit Windows** 

Visit Window Label	Time Interval	Target Day
Baseline	-9 Months - < Day 1	< Day 1
Day 1	Day 1	Day 1
Day 3	Day 2 – Day 5	Day 3
Week 1	Day 6 – Day 10	Day 8
Week 2	Day 11 – Day 20	Day 15
Week 4	Day 21 – Day 36	Day 29
Week 6	Day 37 – Day 59	Day 43
Week 12	Day 60 – Day 127	Day 85
Week 24	≥Day 128	Day 169

## 3.5. Data Handling Rules

In the case where a variable is recorded as ">x", " $\geq$ x", "<x" or " $\leq$ x", for analysis purposes a value of x will be taken. Where a range of values is quoted the midpoint of the range will be taken. For example, if a laboratory safety parameter is reported as being below the limit of quantification or  $\leq$ x, the value of the limit will be used in the calculation of summary statistics. The recorded value will be reported in listings.

## 3.6. Imputation Rules for Missing Adverse Event Dates

Partial adverse event (AE) onset dates will be imputed as follows:

- If the onset date of an AE is only missing the day, it will be imputed as:
- First day of the month that the AE occurred, if month/year of the onset of the AE is different than the month/year of ATIMP administration
- The day of ATIMP administration, if the month/year of the onset of AE is the same as month/year of ATIMP administration and month/year of the AE resolution date is different
- The day of ATIMP administration or day of AE resolution date, whichever is earliest, if month/year of the onset of AE and month/year of ATIMP administration and month/year of the AE resolution date are same
- If the onset date of an AE is missing both day and month, it will be imputed to the earliest of:
- January 1 of the year of onset, as long as this date is on or after ATIMP administration
- Month and day of ATIMP administration, if this date is the same year that the AE occurred
- Last day of the year if the year of the AE onset is prior to the year of ATIMP administration,
- The AE resolution date.
- Completely missing onset dates will not be imputed.

Partial AE resolution dates not marked as ongoing will be imputed as follows:

- If the resolution date of an AE is missing day only, it will be set to the earliest of the last day of the month of occurrence of resolution or the day of the date of death, if the death occurred in that month.
- If the resolution date of an AE is missing both day and month, it will be set to the earliest of December 31 of the year or the day and month of the date of death, if the death occurred in that year.

Completely missing resolution dates will not be imputed.

#### 4. PARTICIPANT INFORMATION

Summary statistics (arithmetic mean, standard deviation [SD], median, minimum and maximum for continuous variables) will be presented by age group and dose level. Frequency tables for categorical data will also be provided overall, and by age group and dose level.

# 4.1. Demographics and Baseline Characteristics

Table 2 list the demographic and baseline characteristic variables that will be summarized by age group, dose level (see Table 3) and overall.

Table 2: Demographic Variables and Baseline Characteristics

Continuous Variables:	Summary Type
Age (years)	Description statistics (N. mass
Weight (kg)	Descriptive statistics (N, mean, SD, median and range
Height (cm) 2	SD, median and range   [minimum and maximum]).
Body Mass Index (BMI) (kg/m )	– [minimum and maximum]).
Categorical Variables	
Age group (children, adults)	
Sex (male, female)	Frequency distribution with the number and percentage of participants in each category.
Race a (American Indian or Alaska Native, Asian, Black or	
African American, Native Hawaiian or other Pacific	
Islander, White, Multiple)	
Ethnicity (Hispanic or Latino, not Hispanic or Latino)	
Study Eye (left, right)	

If multiple race categories are indicated the Race is recorded as 'Multiple'.

# 4.2. Definition of Subgroups

Descriptive summaries of safety and/or efficacy may be done by considering, but not limited to, the following subgroups:

**Table 3: Subgroups** 

Subgroup	Definition
Age group	
 
Adults
 
Children (<16 years old [United Kingdom] or <18 years old [United States])
 

Dose Level	• Low
	Intermediate
	• High
Sex	Female
	Male

## 4.3. Disposition Information

A participant will be considered to have completed the study if the participant completes the Week 24 visit.

The number of participants in the following disposition categories will be summarized throughout the study by age group, dose level and overall for safety analysis set.

- Participants who were administered ATIMP
  - Participants who completed the study
  - Participants who prematurely discontinued from the study and their reasons for discontinuation

Listings will also be provided.

# 4.4. Genetic Testing

A listing of genetic testing data based on screening for CNGA3 mutations prior to enrollment will be provided.

#### 4.5. ATIMP Administration

ATIMP administration volume and study eye data will be summarized. All ATIMP administration data will be listed.

# 4.6. Medical History and Ophthalmic History

Medical history findings will be summarized using Medical Dictionary for Regulatory Activities (MedDRA) by Primary System Organ Class/High Level Term.

Ophthalmic history apart from the study condition will be summarized and an accompanying listing will be provided.

#### 4.7. Prior and Concomitant Medications

Prior and concomitant medications will be coded using the World Health Organization Drug Dictionary (WHO-DD). Prior medications are defined as any therapy initiated before the day of ATIMP administration. Concomitant medications are defined as any therapy used on or after the day of ATIMP administration, including those that started before and continue on or after ATIMP administration.

Summaries of prior and concomitant medications by Anatomical Therapeutic Chemical (ATC) term will be presented by dose level, age group and overall. The proportion of participants who receive each medication will be summarized as well as the proportion of participants who receive at least 1 medication. Supportive listings will be provided.

Concomitant medications of interest (e.g., medication for management of inflammation/corticosteroids) will also be provided.

#### 4.8. Protocol Deviations

Participants with major protocol deviations will be summarized and an accompanying listing will be provided.

#### 5. SAFETY ANALYSES

# 5.1. Primary Safety Outcome

The proportion of participants who experience the primary safety outcome and the corresponding 95% confidence interval (CI) using for the binomial proportion based on the normal approximation with continuity correction will be provided (by age group, dose level and overall). The primary safety outcome will also be listed.

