## **Gene Therapy for Achromatopsia (CNGA3)**

---

In this dose escalation study, up to 18 participants will be administered one of 3 different doses of the ATIMP in cohorts of 3 participants at a time in the first instance. Based on emerging safety data, the SDMC will make a recommendation on the dose to administer to the next cohort of participants. The SDMC may recommend additional participants at a given dose before making their recommendation on how to proceed to the next dose.

Paediatric cases for the purposes of this protocol are defined as participants aged up to and inclusive of 15 years.

In addition to the paediatric cohorts in the UK, an additional cohort of 2 adult subjects will be enrolled in the US. The adult cohort will be administered the highest dose studied from the paediatric cohorts based on when the first adult subject is identified and ready to be enrolled. The SDMC will review the data from all subjects (paediatric and adult) in this dose escalation study.

Safety and efficacy will be assessed for 6 months following the intervention by clinical examination and special investigations according to the schedule in section 5.6 of the protocol. The totality of the data from paediatric subjects enrolled in the UK and adult subjects enrolled in the US will be reviewed and inform the design of a future Phase II interventional study.

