### 4.3.2.2.2.4 Adult Cohort-United States

In addition to the paediatric cohorts in the United Kingdom an additional cohort of 2 adult subjects, 18 years of age or older will be administered ATIMP at the highest dose studied from the paediatric cohorts based on when the first adult subject is identified and ready to be enrolled. The SDMC will also review the data from the adult cohort.

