### 4.3.2.2.5 Additional considerations

In the event of a DLE in one of the participants at a given dose, the cohort may be expanded at the same dose level. The SDMC will review the safety data and recommend that additional participants may be treated at this dose. The SDMC may recommend that the same dose of ATIMP is administered to additional participants. The dose escalation will continue until SDMC are comfortable on review of the accumulating data, to recommend a maximum dose to be administered, or 3 participants have been administered the highest dose without any DLEs, or until at least 2 participants among a cohort of 3 to 6 participants experience DLEs (i.e.,  $\geq 33\%$  of patients with a DLE at that dose level), in which case the recommended dose will be the level below this dose. In the event that 1 or 2 DLEs are seen at the first dose level, the SDMC may recommend administering a lower dose to that described in the protocol to a cohort of participants.

Table 1: Dose escalation table

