#### **5.10.3.2 Statistical Methods – Primary Outcome Analysis**

The primary outcome is safety of subretinal administration of the ATIMP defined as any of the below occurring during the 6 weeks following administration, at least possibly related to the ATIMP, not surgery alone:

- Reduction in visual acuity by 15 ETDRS letters or more that fails to resolve to within 15 letters of baseline in a 4-week period once prophylactic treatment commences
- Severe unresponsive inflammation
- Infective endophthalmitis
- Ocular malignancy
- Grade III or above non-ocular SUSAR (see section 5.11.3)

The number of DLEs at each dose level will be summarised by cohort and overall.

It is anticipated that the ATIMP will be administered at the MTD in up to 18 participants. Safety data relating to these participants will allow estimation of an upper bound for the true event rate through a 95% confidence interval.

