# 1.2. Trial Design

This is an open-label, non-randomized phase I/II dose-escalation trial to determine the safety and efficacy of subretinal administration of the study agent (ATIMP) in participants with CNGA3-related Achromatopsia. In this dose escalation study, up to 18 participants were administered one of 3 doses of the ATIMP in cohorts of 3 pediatric participants at a time in the first instance. Based on emerging safety data, the Safety and Data Monitoring Committee (SDMC) will make a recommendation on the dose to administer to the next cohort of 3 participants.

Pediatric cases for the purpose of the protocol are defined as participants <16 years in the UK or <18 years in the US.

Safety and efficacy will be assessed for 6 months following the intervention by clinical examination and special investigations according to the schedule in Section 5.6 of the protocol. In line with current CHMP and FDA guidance, the ATIMP safety is further assessed by a separate longer term follow up study of 60 months duration, if the participants / caregiver's consent and only once they have reached the 6-month timepoint in the current study.

Due to the rare nature of the disease, there were no formal sample size calculations performed and no formal hypothesis testing is planned.

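### The planned 95% interval for the primary safety outcome shrinks to 1/(2n) when a group has no events: 16.7% after 0/3, where the exact upper limit is 70.8%

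*SAP*

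**What the plan says.** SAP 5.1 reports the proportion of participants with the primary safety outcome and a 95% interval, "using for the binomial proportion based on the normal approximation with continuity correction will be provided", by age group, by dose level and overall. It gives no formula, no exact or score alternative and no rule for groups without events. SAP 1.2 adds that there were "no formal sample size calculations performed and no formal hypothesis testing is planned".

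Protocol 5.10.3.2 names no method but gives the purpose: "Safety data relating to these participants will allow estimation of an upper bound for the true event rate through a 95% confidence interval". The sentence before it reads "It is anticipated that the ATIMP will be administered at the MTD in up to 18 participants".

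The groups are small. Under Protocol 4.3, "up to 18 participants will be administered one of 3 different doses of the ATIMP in cohorts of 3 participants". Expansion is possible: "The SDMC may recommend additional participants at a given dose before making their recommendation". Protocol 4.3.2.2.5 lets escalation run "until at least 2 participants among a cohort of 3 to 6 participants experience DLEs", and another of its end conditions is three participants at the highest dose with no dose-limiting event (DLE). In the US, "an additional cohort of 2 adult subjects, 18 years of age or older will be administered ATIMP at the highest dose studied". SAP 2.1 states that the primary safety outcome uses the same criteria as the DLE.

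**The concern.** The normal approximation takes its width from p(1−p)/n, which is zero when no events are seen. What remains is the continuity correction, which carries no information about the confidence level. A DLE-free cohort of three lets escalation proceed, and three clean participants at the highest dose can end it. Because the outcome and the DLE share criteria, 0/3 is an expected entry in the primary safety table.

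With no hypothesis test planned, this interval is the only planned statement of uncertainty for the primary outcome. The error is on the unsafe side: the printed limit excludes event rates that the data cannot exclude. The results are meant to inform a later Phase II study, mostly from treated children, so a reader could carry an unsupported upper limit forward.

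**Working it through.** **Inputs.** Method, 95% level and reporting groups: SAP 5.1. The interval is taken as two-sided; SAP 6 says so for efficacy, and SAP 5.1 names no one-sided bound. Group sizes: 3 per cohort (Protocol 4.3, SAP 1.2), 3 to 6 if expanded (Protocol 4.3.2.2.5), 2 US adults (Protocol 4.3), up to 18 overall (Protocol 5.7). Derived sizes: 3+2 = 5, 6+2 = 8, 9+2 = 11, and 18+2 = 20 if the adults are counted outside the 18. The plan states no numerical limit, so there is no figure to reproduce.

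**Formulas.** With p = x/n:

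- SAP method, read as corrected Wald: p ± [1.96·√(p(1−p)/n) + 1/(2n)]. At x = 0 the upper limit is exactly 1/(2n).
- Exact two-sided Clopper-Pearson at x = 0: upper limit 1 − 0.025^(1/n).

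For n = 3: 1/6 = 16.7%, against 1 − 0.025^(1/3) = 70.8%.

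| Events/n | SAP upper limit | Exact upper limit |
|---|---|---|
| 0/2 | 25.0% | 84.2% |
| 0/3 | 16.7% | 70.8% |
| 0/5 | 10.0% | 52.2% |
| 0/6 | 8.3% | 45.9% |
| 0/8 | 6.3% | 36.9% |
| 0/11 | 4.5% | 28.5% |
| 0/18 | 2.8% | 18.5% |
| 0/20 | 2.5% | 16.8% |

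A one-sided 95% exact bound is still far above the SAP figure: 63.2% at 0/3 and 15.3% at 0/18.

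**True confidence of the zero-event limit.** If the true rate equals 1/(2n), the chance of no events is (1 − 1/(2n))^n. At n = 3 this is (5/6)³ = 57.9%, so as a one-sided bound the limit has confidence 1 − 0.579 = 42.1%. It is 43.8% at n = 2, 40.7% at n = 6 and 39.8% at n = 18.

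**With one event.** At 1/3: 0.333 ± [1.96·√(0.2222/3) + 0.1667] = 0.333 ± 0.700, that is −36.7% to 103.3%, against 0.8% to 90.6% exact. At 1/6 the upper limit is 54.8% against 64.1%. At 1/18 it is 18.9% against 27.3%.

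**Coverage.** At n = 3 and a true rate of 20%, the interval misses at x = 0 (upper limit 16.7%) and at x = 3 (lower limit 83.3%). Coverage is P(1) + P(2) = 3(0.2)(0.64) + 3(0.04)(0.8) = 48.0%. At a true rate of one third it is 4/9 + 2/9 = 66.7%. Other values:

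- n = 6: 46.7% at a true rate of 10%.
- n = 11: 43.1% at 5%, 68.3% at 10%, 90.2% at 20%.
- n = 18: 60.3% at 5%, 84.9% at 10%, 94.4% at 15%.

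Coverage is about 100% where the true rate lies below 1/(2n), for example 10% or 15% at n = 3 and 2% at n = 18. The exact interval covers at least 95% at every point computed.

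**Against the protocol's own benchmark.** Protocol 4.3.2.2.5 glosses its escalation limit as 33% or more of participants with a DLE. An upper limit of 16.7% after 0/3 would appear to exclude that rate, yet at a true rate of one third 0/3 occurs with probability (2/3)³ = 29.6%.

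**The 18 at the MTD.** Protocol 4.3 and 5.7 give 18 as the total, and the current design text in 4.3 and 4.3.2.2 describes no expansion stage. If the MTD is the highest of three doses and each lower dose takes three participants, at most 18 − 3 − 3 = 12 could receive it, or 14 if the two adults are additional and receive that dose.

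**The case against.** **No trial decision uses the interval.** Escalation and stopping rest on DLE counts and the judgement of the monitoring committee, the analysis is descriptive, and events are listed beside the interval. This stands and limits the harm to reporting. But the listing does not correct a wrong 95% limit. The 33% figure is likewise a gloss on a count rule. No document compares the interval with it, so it serves only as an illustration.

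**The method is inferred.** The SAP sentence appears to lack words, no formula is given, and SAP 1 refers to a separate document of programming instructions that is not available here. If a continuity-corrected score interval was meant, the zero-event upper limits are 69.0% at n = 3 and 21.9% at n = 18, and the fault goes away. Corrected Wald is nevertheless the ordinary meaning of the phrase. The two readings differ about fourfold at 0/3, so the SAP must name the method in any case.

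**0/3 is an extreme case, and the protocol speaks of the MTD group.** The contrast is indeed sharper at small n. It remains large at the larger sizes: 4.2% against 26.5% at n = 12, and 2.8% against 18.5% at n = 18. SAP 5.1 itself orders the interval by dose level and age group.

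**Coverage is not poor everywhere, and the exact interval is conservative.** Both are true. The plan gives no expected event rate that would place the trial in the favourable range, and conservatism is the safer direction for an upper bound on harm. Other sound small-sample intervals would also do.

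**Conclusion.** The concern holds. Under the ordinary reading of SAP 5.1, the interval cannot provide the upper bound that Protocol 5.10.3.2 asks of it. At zero events it understates the exact two-sided limit by 54.1 percentage points at n = 3 (70.8 − 16.7) and by 15.7 at n = 18 (18.5 − 2.8). The fault is worst at zero events, moderate at 1/6 and 1/18, and gives limits outside 0 to 100% at 1/3. It affects the reported precision of the primary outcome, not a type I error rate or an escalation decision. The conclusion rests on the corrected Wald reading and on a two-sided 95% level. It does not depend on whether the two adults count within the 18.

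The statement about 18 participants at the MTD is a separate, smaller error. It overstates the precision available at that dose but does not itself lower the reported bound.

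**What to change.** In SAP 5.1, replace the method with an exact (Clopper-Pearson) two-sided 95% confidence interval for every age group, every dose level and overall. If a score interval was intended, name it and its correction explicitly; the exact interval is the simpler choice at these sizes.

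In Protocol 5.10.3.2, say that up to 18 is the total over all doses. A dose level would hold about 3 to 6 children, or about 5 to 8 participants where the two US adults receive that dose, and more if the monitoring committee adds participants. The mention of dose confirmation under Study Type in Protocol 1.3 should be reconciled at the same time. Quoting exact zero-event upper limits would show the precision to expect: 70.8% at n = 3, 52.2% at 5, 45.9% at 6, 36.9% at 8, 26.5% at 12, 23.2% at 14 and 18.5% at 18. These figures are useful but not essential to the repair.

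The cost is one SAP sentence, one software option and one short protocol correction, with no new data and no design change. The reported bounds will be wider and somewhat conservative.

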#### 5.2. Adverse Events

The verbatim terms used in the eCRF by investigators to identify adverse events will be coded using the Medical Dictionary for Regulatory Activities (MedDRA) at the time of database lock. Any AE occurring on or after the initial administration of ATIMP is considered to be treatment-emergent. All reported treatment-emergent adverse events will be included in the analysis. For each adverse event, the number and percentage of participants who experience at least 1 occurrence of the given event will be summarized by age group, dose level and overall.

Summary tables (count, frequency) will be provided for the frequency and incidence of participants experiencing the following treatment-emergent adverse events:

- AEs
- Serious AEs (SAEs)
- AEs leading to termination of study participation
- AEs by severity
- AEs by relationship to ATIMP
- AEs by relationship to ATIMP surgery
- Death
- AEs of interest related to ocular inflammation

Summaries of adverse events by system organ class and dictionary-derived (preferred) term will also be provided.

In addition to the summary tables, accompanying listings will be provided for subjects who experience:

- AEs
- SAEs
- AEs leading to termination of study participation

10

- Death (if any)
- AEs of interest related to ocular inflammation.

# 5.3. Clinical Laboratory Tests

Clinical laboratory tests will be displayed for the participants included in the safety analysis set. Hematology, clinical chemistry, glucose, serology and polymerase chain reaction (PCR) laboratory tests will be presented.

Summary statistics of hematology and clinical chemistry observed values and change from baseline by parameter (unit) will be summarized by age group, dose level and overall.

All hematology and clinical chemistry values will be listed.

Serology data will be listed and summarized at each assessment by age group, dose level and overall.

All PCR values will be summarized by tissue and listed.

## 5.4. Vital Signs and Physical Examination Findings

Continuous vital sign parameters including height, weight, pulse, blood pressure (systolic and diastolic), pulse, respiration rate, arterial oxygen saturation, temperature will be summarized at each assessment time point. Change from baseline will be summarized through Week 24 using descriptive statistics (mean, standard deviation, median, minimum and maximum).

Individual physical examination data will be listed by participant.

# 5.5. Other Safety Parameters

All pregnancy test data will be listed.

#### 6. EFFICACY

Unless otherwise specified, efficacy analyses will be based on the full analysis set and confidence intervals will be presented at a 2-sided level of 95%.

#### 6.1. Analysis Methods

Summaries by age group, dose level and time point (and study eye when appropriate) using descriptive statistics will be provided for each outcome. Descriptive statistics such as mean, median, standard deviation, minimum, and maximum will be used to summarize continuous variables, and counts and percentages will be used to summarize categorical variables; 95% CIs may be provided for descriptive statistics. Data from each individual will also be plotted across time by age group and dose level for the treated eye compared to the untreated eye, if available. Change from baseline will be summarized, if appropriate.

Mixed models for repeated measures may be used to estimate change from baseline in selected efficacy parameters for the treated eye adjusted for baseline value, dose level, visit and the interactions of dose level by visit and baseline by visit. An unstructured correlation structure will

be used to model within-subject correlations when possible. Possible transformations of the response (i.e., logarithm) may also be considered for some outcomes.

Sensitivity analyses with demographics such as sex and race may be explored.

Quality of life patient reported outcome measures will be analyzed through descriptive statistics and may be also used to correlate a participant's feeling about their own well-being with clinical observations. The IVI-C and IVI-A will be summarized by the 3 domains of reading and accessing information, mobility and independence, and emotional well-being. The EQ-5D-5L and EQ-5D-Y will also be summarized (see Attachment 1 for details).

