**Gene Therapy for Achromatopsia (CNGA3)**

	
 
• Participated in another research study involving an investigational therapy for ocular disease within the last 6 months
 
• Use of high dose regular non-steroidal anti-inflammatory drugs at the time of screening
 
• Have any other condition that the Principal Investigator (PI) considers makes them inappropriate for entry into the trial
 
• Are unwilling to consider the possibility of entry into a subsequent longer term follow up study
 
• During the 6 weeks prior to baseline, have had any confirmed SARS-CoV-2 (COVID-19) infection
 

Study Type	Phase I/II, open-label, non-randomised, multi-centre, dose escalation study, followed by dose confirmation in children with Achromatopsia owing to defects in CNGA3
Date of First Enrolment	Anticipated Q1 2019
Target Sample Size	Up to 18 participants
Primary Outcome(s)	
The primary outcome is safety of subretinal administration of AAV8-hG1.7p.coCNGA3.
 
Safety is defined as the absence of ATIMP-related:
 
 
• Reduction in visual acuity by 15 ETDRS letters or more that fails to resolve to within 15 letters of baseline in a 4-week period once prophylactic treatment commences
 
• Severe unresponsive inflammation
 
• Infective endophthalmitis
 
• Ocular malignancy
 
• Grade III or above non-ocular SUSAR
 
 
Safety will be assessed for 6 months after the intervention in this study, and a further optional 4.5 years in a separate subsequent study.

Key Secondary Outcomes	
The secondary outcomes are measures of the efficacy of the intervention, which will be performed on an individual participant basis and will be descriptive in nature. Efficacy will be assessed at several time points between 3 to 6 months after the intervention:
 
 
1) Any improvement in visual function from baseline that is greater than the baseline variation for that test and is sustained for at least two consecutive assessments.
 
2) Any improvement in retinal function from pre-intervention that is greater than the baseline variation and measurable by electroretinography (ERG).
 
3) Quality of life measures including EQ-5D and IVI or equivalent as appropriate.
 

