### 4.1.6 Explanation for Choice of Comparators

There is no currently approved treatment for Achromatopsia caused by mutations in *CNGA3*. The comparator will be the contralateral eye and supplementary data collected as part of a prospective, parallel natural history study of patients with Achromatopsia.

The totality of the data from paediatric subjects enrolled in the UK and adult subjects enrolled in the U.S. will be reviewed and inform the design of a future Phase II interventional study.

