### 5.5.2 Secondary Outcomes

The secondary outcomes are measures of the efficacy of the ATIMP; these will be performed on an individual participant basis and will be descriptive in nature.

- Any improvements in visual function from baseline that are greater than the baseline variation and are sustained for at least two consecutive assessments.
- Any improvement in retinal function from pre – intervention that is greater than the baseline variation and measurable by electrophysiology (pattern ERG or full-field ERG). Quality of life will be measured by the Impact of Visual Impairment (IVI) questionnaire and the EQ5D-5L and EQ5D-Y, or equivalent as appropriate.

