### **CNGA3CNGA3 Gene Therapy trial for Achromatopsia**

---

2) Any improvement in retinal function from pre – intervention assessment that is greater than baseline variation and measurable by electrophysiology (pattern ERG or full-field ERG).

Measures will be reported individually and aggregated across participants as the proportion who satisfy the above criteria.

Quality of life patient reported outcome measures will be used to correlate a participant’s feeling about their own wellbeing with clinical observations.

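### ERG improvement must exceed baseline variation, but only one ERG is scheduled before treatment and neither the protocol nor the SAP text names another limit

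*SAP*

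**What the plan says.** **ERG criterion.** Protocol 1.3 reads "Any improvement in retinal function from pre-intervention that is greater than the baseline variation and measurable by electroretinography (ERG"). Section 5.5.2 has "greater than the baseline variation and measurable by electrophysiology (pattern ERG or full-field ERG") and section 5.10.3.3 has "greater than baseline variation and measurable by electrophysiology (pattern ERG or full-field ERG"). Efficacy is to be evaluated for each participant separately (1.3, 5.5.2, 5.10.3.3), and then: "Measures will be reported individually and aggregated across participants as the proportion who satisfy the above criteria".

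**Schedule.** Protocol Table 2 marks pattern and full-field ERG at screening and at W24 only, with no mark in the three baseline columns. Section 5.3.1.6.2 lists electrophysiology as a screening test. Section 5.3.1.6.3 exempts it from repetition when dosing is delayed.

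**Other tests.** Visual acuity, colour vision, contrast sensitivity, reading, static perimetry, full-field stimulus testing and photoaversion have three baselines and are tested at W12 and W24. Protocol 5.4.2.1 says repeated baselines are there to allow for test-retest variability. SAP 3.2 takes their arithmetic mean as the baseline value.

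**SAP analysis.** Section 6.1 gives "Summaries by age group, dose level and time point (and study eye when appropriate) using descriptive statistics will be provided for each outcome", individual plots "for the treated eye compared to the untreated eye, if available", and an optional mixed model "for the treated eye adjusted for baseline value, dose level, visit and the interactions of dose level by visit and baseline by visit". It contains neither the improvement criteria nor the proportion meeting them.

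**The concern.** A criterion that compares a change with a participant's own baseline variation needs at least two baseline values. ERG has one. The criterion therefore cannot be scored from the planned data unless another source for the limit is named, and none is.

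For the other tests the data exist but the rule does not. The centre is fixed (the baseline mean), while the margin that counts as variation is left open. A margin chosen after the results are known can change the responder count considerably, and the trial is open-label.

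The stake is not a false-positive hypothesis test, because none is planned. It is a responder count that readers cannot interpret, in data that protocol 4.3 says will inform the design of a Phase II study.

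**Working it through.** The plan states no threshold, test-retest figure or sample-size calculation, so there is no figure of its own to reproduce. The rates below are illustrations under stated assumptions.

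**1. ERG: degrees of freedom.** Pre-treatment ERGs per participant: n = 1. A standard deviation has n − 1 = 0 degrees of freedom and is undefined; the range is 0.

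**2. ERG: variation read as zero.** Any rise from screening to W24 then counts. With no effect and symmetric error, P(W24 value > screening value) = 1/2 for one ERG parameter. That is 18 × 0.5 = 9 participants at the maximum enrolment, or 11 × 0.5 = 5.5 if no cohort is expanded (3 cohorts of 3, plus 2 adults).

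**3. Other tests: effect of the unstated margin.** Assumptions: no effect, three baselines and two follow-ups (W12 and W24, the assessments in the 3-to-6-month efficacy period), independent normal errors with equal SD. A hit means that both follow-ups exceed the threshold. Simulation of 1,000,000 participants:

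| Threshold, own baselines only | Chance hit |
|---|---|
| Best of the 3 baselines | 10.0% (exact: 1/C(5,2) = 1/10) |
| Mean + 1 SD | 9.3% |
| Mean + range | 3.9% |
| Mean + 2 SD | 3.6% |
| Mean + 1.96 × √2 × SD | 2.1% |

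The ratio of the extremes is 10.0/2.1 = 4.8, about 5-fold. In 18 participants this is 1.8 against 0.4 expected chance responders per test.

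**4. A limit for ERG that can be computed.** Take the screening-to-W24 change in the untreated eyes, pooled over participants. The upper 95% prediction limit is mean + k × SD, with k = t(0.975, n − 1) × √(1 + 1/n).

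- n = 18: k = 2.110 × 1.027 = 2.17
- n = 11: k = 2.228 × 1.044 = 2.33

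Simulated properties, in units of the SD of change:

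| | 18 eyes | 11 eyes |
|---|---|---|
| False hit, no effect | 2.5% | 2.5% |
| 5-95% range of the limit | 1.4 to 2.9 | 1.3 to 3.3 |
| Hit rate, true gain of 2 SD | 45% | 41% |
| False hit if treated-eye change is 1.25 times as variable | about 5% | about 5% |

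These figures assume normal changes, independent between eyes, with the same distribution in treated and untreated eyes when there is no effect.

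**5. Two candidate rules for the other tests**, both follow-ups required, same assumptions as step 3:

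| Threshold | Chance hit | Hit rate, true gain of 2 test-retest SD |
|---|---|---|
| Best of 3 | 10% | 71% |
| Mean + 1.96 × SD pooled over 18 participants (18 × 2 = 36 df) | 0.6% | 31% |

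A strict margin costs a good deal of sensitivity, so the choice is a trade-off and no rule is clearly right.

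**The case against.** **The criterion need not mean own variation.** The protocol does not use the word own, has electrophysiology consultants interpret the ERG (5.4.2.1), and refers to established methods of analysis (5.10.3.3). A pooled, fellow-eye or external limit would satisfy the wording. This stands in part: the gap can be closed by a definition. But evaluation is per participant, no such limit is named, and an appeal to expert methods supplies no threshold.

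**The rule may be in a document not supplied.** SAP section 1 places mock-ups and programming instructions elsewhere, and protocol 5.4.2.1 refers to a study manual. This stands as a caveat on the other tests. It would not give ERG a second baseline.

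**Efficacy is secondary and descriptive.** True, and it limits the severity. A descriptive proportion still needs a definition.

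The documents do not support three stronger readings that a reader might infer:

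- *That an old screening ERG falls outside the SAP's baseline window and is lost.* SAP 3.4 applies its windows to visits other than baseline. SAP 3.2 admits a screening value when no other exists and sets no age limit.
- *That the open threshold moves the count about 20-fold.* That sets best of 3 (10%) against a known SD (0.5%), and the documents give no known SD.
- *That omitting a paired between-eye estimate is an error.* Protocol 4.1.6 says "The comparator will be the contralateral eye and supplementary data collected as part of a prospective, parallel natural history study of patients with Achromatopsia", but promises no paired estimate, and SAP 6.1 already provides by-eye summaries when appropriate and plots of both eyes. Pairing removes a shift shared by both eyes. However, the treated eye is the poorer-seeing one (5.4.2.2.2), so pairing can also double the regression to the mean: about 0.29 against 0.15 test-retest SD. That assumes the eye is chosen on the three-baseline mean of the same test, with a between-eye error correlation of 0.5 and an eye-specific SD of 0.5.

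**Conclusion.** The ERG point holds. The protocol states a per-participant criterion in three sections that the scheduled single pre-treatment ERG cannot support, and no substitute limit appears in the protocol or SAP text. Under the zero-variation reading, about 50% of participants with no effect would count as improved on a given parameter.

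The secondary point holds for the text supplied. The margin for the other tests is undefined, with about a 5-fold spread in chance hits among own-baseline rules, and the responder proportion has not been carried into SAP section 6. The 5-fold figure rests on independent normal errors and three separate baselines. Same-day baselines, which Table 2 footnote 1 allows, may miss day-to-day variation.

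This should be corrected before database lock, but it does not threaten the primary safety outcome.

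**What to change.** **1. ERG (SAP section 6).** Score improvement against the 95% prediction limit of the screening-to-W24 change in untreated eyes, pooled over participants (mean + 2.17 SD with 18 eyes, + 2.33 SD with 11), or against a named external limit. Name one pattern ERG and one full-field ERG parameter, each with its direction of improvement; where improvement is a fall, subtract instead of adding. If either parameter may count, state that the false-hit rate is at most 2 × 2.5% = 5%. Align the wording of protocol 1.3, 5.5.2 and 5.10.3.3 at the next amendment.

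**2. Other tests.** Before database lock, fix one threshold per test with its direction, state its chance-hit rate and its sensitivity, and add the responder proportion of protocol 5.10.3.3 to the SAP.

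**Optional.** A paired treated-minus-untreated change may be added as a description, with the regression-to-the-mean caveat.

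**Cost.** SAP text and programming on data already scheduled, with no extra visit or ERG, plus a wording change in three protocol sections. The pooled ERG limit is imprecise and misses more than half of true 2-SD gains. It needs both eyes recorded, and it mixes ages and recording conditions (anaesthesia, modified protocols in young children).
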